4.4. Independent Data Monitoring Committee

An IDMC will be established by charter to provide independent review and assessment of study data and to monitor the overall study conduct in a systematic manner to safeguard the safety of study subjects. Periodic meetings will occur as outlined in the IDMC charter. An interim analysis, which will be reviewed by the IDMC, will be performed when approximately 60 subjects with an MRI-PDFF value of $\geq 8\%$ liver fat at Baseline have completed the Week 26 visit or an Early Termination Visit after Week 22. The IDMC will be provided with selected biomarker and safety interim results to allow for a more complete examination of the totality of the data. Upon review of the interim analysis findings, the IDMC may communicate with the Sponsor by making recommendations to the Sponsor to continue, amend, or stop the study based on these interim analysis results. The Sponsor will maintain its blind to any individual treatment assignments.

4.5. Interim Analyses

A single (secondary endpoint) efficacy interim analysis is planned when approximately 60 subjects with an MRI-PDFF value of $\geq 8\%$ liver fat at Baseline have completed Week 26 or an Early Termination visit after Week 22. The purpose of the proposed interim analysis is to examine the TVB-2640 benefit over placebo based on a Week 26 secondary efficacy endpoint consisting of "proportion of MRI-PDFF $\geq 30\%$ responders at Week 26, where an MRI-PDFF $\geq 30\%$ responder is defined as a subject with $\geq 8\%$ liver fat content at Baseline who achieves a percent change (reduction) from Baseline in MRI-PDFF $\geq 30\%$ ".

Interim safety summaries will accompany the interim analyses of the secondary efficacy endpoint.

An interim analysis of the primary efficacy endpoint is not feasible since the primary endpoint is only evaluated at Week 52, and not at Week 26. Therefore, a statistical penalty is not envisaged in conjunction with the Week 26 interim analysis of the above-stated secondary endpoint.

5. STUDY ENDPOINTS

5.1. Efficacy

The co-primary efficacy endpoints are the proportion of subjects experiencing the following:

- Histological improvement at Week 52 in NAS (i.e., ≥ 2 -point improvement in NAS with ≥ 1 -point improvement in ballooning or inflammation) and without worsening of fibrosis score (by NASH CRN fibrosis score)
- Resolution of steatohepatitis and no worsening of liver fibrosis (by NASH CRN fibrosis score). Resolution of steatohepatitis is defined as absence of fatty liver disease or isolated or simple steatosis without steatohepatitis and a NAS of 0 or 1 for inflammation, 0 for ballooning, and any value for steatosis

AND

Histological improvement in NAS (≥ 2 points improvement in NAS) at Week 52.

The secondary efficacy and pharmacodynamic endpoints are:

- Proportion of MRI-PDFF $\geq 30\%$ responders at Week 26, where an MRI-PDFF $\geq 30\%$ responder is defined as a subject with $\geq 8\%$ liver fat content at Baseline who achieves a relative reduction from Baseline in MRI-PDFF $\geq 30\%$.
- Proportion of MRI-PDFF $\geq 30\%$ responders at Week 52 where an MRI-PDFF $\geq 30\%$ responder is defined as a subject with $\geq 8\%$ liver fat content at Baseline who achieves a relative reduction from Baseline in MRI-PDFF $\geq 30\%$.
- Proportion of MRI-PDFF $\geq 50\%$ responders at Week 52 where an MRI-PDFF $\geq 50\%$ responder is defined as a subject with $\geq 8\%$ liver fat content at Baseline who achieves a relative reduction from Baseline in MRI-PDFF $\geq 50\%$.
- Proportion of subjects with improvement in liver fibrosis ≥ 1 stage by NASH CRN fibrosis score (without worsening of steatohepatitis (defined as no increase in NAS for ballooning, inflammation, or steatosis) at 52 weeks.
- Proportion of subjects with improvement in liver fibrosis ≥ 1 stage by NASH CRN score without increase of total NAS score at Week 52.
- Proportion of subjects with improvement in liver fibrosis ≥ 1 stage by NASH CRN score without any worsening of NASH (defined as no worsening of ballooning and lobular inflammation; a 1 grade change in steatosis may be acceptable) at Week 52.
- Proportion of subjects experiencing **both** of the following at Week 52:
 - Resolution of steatohepatitis on overall histopathological reading and no worsening of liver fibrosis on NASH CRN fibrosis score. Resolution of

steatohepatitis is defined as absent fatty liver disease or isolated or simple steatosis without steatohepatitis and a NAS score of 0-1 for inflammation, 0 for ballooning, and any value for steatosis.

AND

- Improvement in liver fibrosis greater than or equal to one stage (NASH CRN fibrosis score) and no worsening of steatohepatitis (defined as no increase in NAS for ballooning, inflammation, or steatosis).
- Proportion of subjects experiencing **both** of the following at Week 52:
 - Histological improvement at Week 52 in nonalcoholic fatty liver disease (NAFLD) activity score (NAS) (i.e., ≥ 2 points improvement in NAS with ≥ 1 point improvement in ballooning or inflammation) and without worsening of fibrosis (by NASH Clinical Research Network [CRN] fibrosis score)

AND

- Improvement in liver fibrosis greater than or equal to one stage (NASH CRN fibrosis score) and no worsening of steatohepatitis (defined as no increase in NAS for ballooning, inflammation, or steatosis).
- Proportion of subjects with resolution of steatohepatitis and no worsening of liver fibrosis (by NASH CRN fibrosis score). Resolution of steatohepatitis is defined as absence of fatty liver disease or isolated or simple steatosis without steatohepatitis and a NAS of 0 or 1 for inflammation, 0 for ballooning, and any value for steatosis at Week 52.
- Proportion of subjects with histological improvement (decrease) at Week 52 in NAS by ≥ 1 point.
- Proportion of subjects with histological improvement (decrease) at Week 52 in NAS by ≥ 2 points.
- Change and percent change from Baseline in MRI-PDFF liver fat (%) at Week 26.
- Change and percent change from Baseline in MRI-PDFF liver fat (%) at Week 52.
- Proportion of subjects with NASH resolution (defined as absence of fatty liver disease or isolated or simple steatosis without steatohepatitis and a NAS of 0 or 1 for inflammation, 0 for ballooning, and any value for steatosis) at 52 weeks.
- Change from Baseline in ALT, AST, alkaline phosphatase (ALP), and GGT at Weeks 26 and 52 and at each study visit.
- Change from Baseline in LDL-C and other lipid levels (including LDL/HDL ratio) at Weeks 26 and 52 and at each study visit.
- Change from Baseline in collagen/fibrous area and fibrosis score, assessed by digital pathology, at Week 52.
 - The primary digital pathology variables that will be analyzed include the following:
 - qFibrosis – continuous value

- qFibrosis – stage
- qSteatosis – continuous value
- qSteatosis – grade
- Steatosis corrected qFibrosis – continuous value
- Steatosis corrected qFibrosis – stage
- Change from Baseline in metabolic parameters, including fasting insulin, fasting glucose, HOMA-IR, adipo-IR, and HbA1c levels at Weeks 26 and 52 and at each study visit.
- Change from Baseline in FGF-21, adiponectin, and other NASH biomarker levels at Weeks 26 and 52 and at each study visit.
- Change from Baseline in FibroScan Liver Stiffness Measurement (kPa) and CAP score results at Weeks 26 and 52.
- Change from Baseline in PRO-C3 and other fibrosis biomarkers at Weeks 4, 13, 26, and 52.
- Change from Baseline in ELF score at Weeks 26 and 52.
- Plasma concentrations of TVB-2640 at Weeks 1, 4, 13, 26, and 52.
- Proportion of subjects with histological improvement at Week 52 in NAS (i.e., ≥ 2 points improvement in NAS with ≥ 1 point improvement in ballooning or inflammation) and without worsening of fibrosis (by NASH CRN fibrosis score)
- Proportion of subjects with resolution of steatohepatitis and no worsening of liver fibrosis (by NASH CRN fibrosis score). Resolution of steatohepatitis is defined as absence of fatty liver disease or isolated or simple steatosis without steatohepatitis and a NAS of 0 or 1 for inflammation, 0 for ballooning, and any value for steatosis.

The exploratory efficacy and pharmacodynamics endpoints are:

- Proportion of MRI-PDFF $\geq 30\%$ responders at Week 52 who have ≥ 17 U/L reduction in ALT.
- Change from Baseline in FAST score at Weeks 26 and 52.
- Change from Baseline in Agile 3+ score at Weeks 26 and 52.

The formula from Sanyal et al (2023) for the Agile 3+ score is:

$$\text{Agile 3+} = e^{\text{logit}(p_{F \geq 3})} / (1 + e^{\text{logit}(p_{F \geq 3})})$$

with

$$\text{logit}(p_{F \geq 3}) = -3.92368 + 2.29714 \times \ln(\text{LSM}) - 0.00902 \times \text{PLT} - 0.98633 \times \text{AAR}^{-1} + 1.08636 \times \text{Diabetes status} - 0.38581 \times \text{Sex} + 0.03018 \times \text{Age}$$

Where ln is natural log; LSM=Liver Stiffness Measurement (kPa) by vibration-controlled transient elastography (VCTE); AAR=AST/ALT ratio; PLT=platelets (G/L); Sex: male=1, female=0; and Diabetes status: yes=1, no=0.

- Change from Baseline in levels of select fibrosis biomarkers (e.g., TIMP-1) at Weeks 4,

13, 26, and 52.

- Change from Baseline in levels of lipidomic/metabolomic biomarkers (e.g., tripalmitin, ceramides, bile acids, diacylglycerols, and other classes of metabolites) at Weeks 4, 13, 26, and 52.
- Change from Baseline in HbA1c levels among subjects with T2DM at Weeks 13, 26, 39, and 52.
- Change from Baseline in FIB-4 at Weeks 4, 13, 26, and 52.
- Change from Baseline in additional fibrosis parameters such as zonal analyses of fibrosis, NAS, and individual NAS components as determined by digital pathology at Week 52.
- Correlation of changes in MRI-PDFF with changes in other endpoints.
- Presence or absence of SNPs relevant for NASH.
- Correlation of predictive signature with other endpoints.
- Correlation of lipids (e.g. tripalmitin) with other endpoints.
- Change from Baseline in gut microbiome analyses at Weeks 26 and 52 in a substudy of subjects.
- Change from Baseline in HepVita Nutritional Survey at Weeks 26 and 52 in a substudy of subjects.
- Change in MELD score from baseline to Week 52

The formula from Kamath et al (2001) for the MELD score is $3.8 \times \ln(\text{bilirubin [mg/dL]}) + 11.2 \times \ln(\text{INR}) + 9.6 \times \ln(\text{creatinine [mg/dL]}) + 6.4 \times (\text{etiology: 0 if cholestatic or alcoholic, 1 otherwise})$.

Where \ln is natural log.

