6.2. Endpoints

6.2.1. Primary Efficacy (Responder) Endpoint

The proportion of subjects experiencing either of the following:

- Histological improvement at Week 52 in NAS (ie, ≥ 2 points improvement in NAS with ≥ 1 point improvement in ballooning or inflammation) and without worsening of fibrosis (by NASH CRN fibrosis score)

OR
- Resolution of steatohepatitis and no worsening of liver fibrosis (by NASH CRN fibrosis score). Resolution of steatohepatitis is defined as absence of fatty liver disease or isolated or simple steatosis without steatohepatitis and a NAS of 0 or 1 for inflammation, 0 for ballooning, and any value for steatosis.

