8.1. Subject Inclusion Criteria

Subjects meeting all of the following criteria are eligible for enrollment into the study.

1. Must be willing and able to participate in the study and provide written informed consent.
2. Male and female adults ≥ 18 years of age on the date that written informed consent to take part in the study is provided.
3. Body mass index (BMI) $\geq 23 \text{ kg/m}^2$ for Asians and $\geq 25 \text{ kg/m}^2$ for other races.
4. Female subjects must be either:
 - a. Not of childbearing potential (ie, surgically [bilateral oophorectomy, hysterectomy, or tubal ligation] or naturally sterile [>12 consecutive months without menses]).
OR
 - b. Female subjects of childbearing potential must have a negative serum pregnancy (beta-human chorionic gonadotropin [β -HCG]) test during Screening, a negative urine pregnancy test within 24 hours before the first dose of study drug on Day 1, and must agree to perform urine home pregnancy tests monthly between study visits. Female subjects of childbearing potential must not be breastfeeding, not plan to become pregnant during the study, and must use 2 forms of birth control, one being a barrier method (ie, condoms, diaphragm, IUD) throughout the study and for at least 3 months after the final study drug dose. Hormonal contraception (stable ≥ 3 months) and hormonal IUDs are permitted if used with a secondary barrier birth control method (e.g., condoms).
5. Male subjects who have sexual intercourse with a female partner of childbearing potential from the first dose of study drug until 3 months after completion of study drug intake must be either surgically sterile (confirmed by documented azoospermia >90 days after the procedure) OR agree to use a condom with spermicide. All male subjects must agree not to donate sperm from the first dose of study drug until 3 months after completion of study drug intake.
6. Must have liver stiffness measurement $\geq 8.5 \text{ kPa}$ measured by FibroScan and CAP score measured by FibroScan $\geq 280 \text{ dB/m}$ (unless the enrolling study site does not have the capability to measure CAP) during the Screening period.
7. Histologic confirmation of NASH: must have had a prior liver biopsy within 180 days before the Screening visit, or a new biopsy during the screening period, with fibrosis stage F2-F3 and a NAS of ≥ 4 with at least a score of 1 in each of the following NAS components:
 - a. Steatosis (scored 0 to 3)
 - b. Ballooning degeneration (scored 0 to 2)

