13.2. Efficacy Analysis

13.2.1 Primary Efficacy Endpoint

The primary efficacy endpoint is the proportion of subjects experiencing either a histological improvement at Week 52 in NAS (i.e., ≥ 2 -point improvement in NAS with 1-point improvement in ballooning or inflammation) and without worsening of fibrosis score (by NASH CRN fibrosis score), **OR** resolution of steatohepatitis and no worsening of liver fibrosis (by NASH CRN fibrosis score). Resolution of steatohepatitis is defined as absence of fatty liver disease or isolated or simple steatosis without steatohepatitis and a NAS of 0 or 1 for inflammation, 0 for ballooning, and any value for steatosis.

Subjects will be eligible for analysis of the primary efficacy endpoint if they have completed at least 42 weeks of treatment and have a posttreatment biopsy.

The principal analysis of the primary efficacy endpoint will be based on the Intention-to-Treat (ITT) analysis set (Section 13.4.2). The treatment groups will be compared based on the primary efficacy endpoint using a one-sided Cochran-Mantel-Haenszel (CMH) test stratified by the randomization stratifications T2DM status (yes or no), region (North America or not North

America), and amount of fibrosis (F2 or F3) at the 0.05 significance level (where a higher responder proportion is a better outcome). A Clopper-Pearson 90% and 95% CI will be derived, and the odds ratio (with its 90% and 95% CI, using the control group as a reference group) will be produced to assess the treatment effect magnitude.

Evaluation of the robustness of the principal analysis of the primary efficacy endpoint will be carried out using a logistic regression with response as a dependent variable; treatment group, randomization stratification factors (T2DM status [yes or no], region [North America or not North America], and amount of fibrosis [F2 or F3]) as independent factors; and age as a baseline covariate. Other baseline covariates and other adjustment factors will be prespecified in the statistical analysis plan (SAP). The analysis of the primary efficacy endpoint will be repeated for the modified Intention-to-Treat (mITT) population (Section 13.4.2) to ascertain any changes in the conclusion of the principal analysis findings.

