4.3. Sample Size Considerations

The study is powered to test the one-sided (statistical) superiority hypothesis stipulating that a TVB-2640 50-mg dose provides better benefit than placebo based on the primary efficacy endpoint. The study estimated total sample size is approximately 162 randomized subjects (108 on TVB-2640 and 54 on placebo). The sample size was derived using the normal approximation to the binomial distribution, and the estimated power to detect a difference in the primary efficacy response of 20% (TVB-2640 40% and placebo 20% at Week 52) was at least 80% (one-sided test at the 0.05 significance level). A 2-to-1 randomization allocation was assumed (TVB-2640 to placebo), and an anticipated dropout rate of 18.5% was also applied to estimate the final total sample size (N=162).

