11. CHANGES TO THE PLANNED ANALYSES

The following changes were made to analyses specified in the protocol. Any additional changes to the planned analyses as detailed in this SAP will be described in the CSR.

- Co-primary objectives and endpoints were added.
- Added 'To evaluate the effect of TVB-2640 50 mg QD compared with matching placebo on resolution of steatohepatitis and no worsening of liver fibrosis (by NASH CRN fibrosis score). Resolution of steatohepatitis is defined as absence of fatty liver disease or isolated or simple steatosis without steatohepatitis and a NAS of 0 or 1 for inflammation, 0 for ballooning, and any value for steatosis at Week 52.' as a secondary objective and endpoint.
- Added 'To evaluate the effect of TVB-2640 50 mg QD compared with matching placebo on histological improvement (decrease) at Week 52 in NAS by ≥ 2 points.' as a secondary objective and endpoint.
- Removed 'To evaluate the effect of TVB-2640 50 mg QD compared with matching placebo on fibrosis as assessed by ≥ 1 stage of fibrosis improvement by NASH CRN score without worsening of NAS (defined as no increase in any component of NAS) at Week 52.' as a secondary objective and endpoint.
- Added proportion of MRI-PDFF $\geq 50\%$ responders, MELD, and Agile3+ endpoints.
- Region (North America or not North America) was removed as an effect in all analyses.

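### The Protocol's either/or primary endpoint has no planned test or confidence interval in the SAP, and SAP Section 11 does not say that it was replaced

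*SAP*

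**What the plan says.** **Protocol.** Section 6.2.1 sets a single responder endpoint: "The proportion of subjects experiencing either of the following". Limb A is a NAS fall of at least 2 points, with at least 1 point in ballooning or inflammation and no fibrosis worsening. Limb B is "Resolution of steatohepatitis and no worsening of liver fibrosis (by NASH CRN fibrosis score"), with no condition on the size of the NAS fall. Section 13.2.1 applies the one-sided stratified CMH test to this composite: "The primary efficacy endpoint is the proportion of subjects experiencing either a histological improvement at Week 52 in NAS", or resolution. The combination of limb B with a 2-point NAS fall is a secondary endpoint in Section 6.2.2.

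**SAP.** Sections 3.1, 5.1 and 7.4 give two separate co-primaries. Endpoint 1A is limb A alone. Endpoint 1B is limb B together with "Histological improvement in NAS (≥ 2 points improvement in NAS) at Week 52". Resolution is still defined by "a NAS of 0 or 1 for inflammation, 0 for ballooning, and any value for steatosis". Limb B alone is secondary endpoint 10, and NASH resolution regardless of fibrosis is secondary endpoint 15. The secondary list in 5.1 also repeats limbs A and B, each on its own. The composite A or B is absent from 5.1, 7.2, 7.4 and 9.

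Section 11 records the change as "Co-primary objectives and endpoints were added". Section 4.3 keeps the Protocol's sizing sentence, "the estimated power to detect a difference in the primary efficacy response of 20" percentage points (40% versus 20%), for one primary endpoint.

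**The concern.** The SAP is the basis for the analyses in the study report (SAP Section 2). As it stands, the endpoint that the Protocol names as primary, and for which the 40% and 20% rates were set, would be reported without a test or an interval.

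The record of the change is incomplete. Section 11 states other deletions outright: one fibrosis endpoint and the region factor are both described as removed. For the primary it mentions only an addition, so a reader could think that the either/or endpoint is still there. Section 4.3 supports that impression by sizing a single endpoint.

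The split also changes who counts. Some subjects who are primary responders under the Protocol are responders on neither co-primary.

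**Working it through.** **1. The plan's own sample size.** Inputs from SAP 4.3: 40% versus 20%, one-sided 0.05, 80% power, 2:1 allocation, 18.5% dropout. Normal approximation with unpooled variance:

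- n(placebo) = (0.2×0.8 + 0.4×0.6/2) × (1.645 + 0.842)² / 0.2² = 43.3, rounded up to 44
- total = 44 + 88 = 132, and 132/0.815 = 162, as stated
- power at 88 and 44 evaluable subjects = 80.6%

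The 162 therefore belongs to one endpoint with these rates.

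**2. Score patterns.** Write S, B and I for steatosis (0–3), ballooning (0–2) and lobular inflammation (0–3). Protocol 8.1 requires NAS of at least 4, "with at least a score of 1 in each of the following NAS components".

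- Baseline profiles: 3×2×3 = 18, less S1/B1/I1 (sum 3) = 17
- Week 52 states: 4×3×4 = 48, so 17×48 = 816 transitions
- Resolution states (B = 0, I = 0 or 1, any S): 4×1×2 = 8 per profile, so 17×8 = 136 transitions

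No fibrosis worsening is assumed throughout.

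**3. 1B lies inside 1A.** Baseline B is at least 1 and resolution needs B = 0, so every resolver has a ballooning fall of at least 1. Adding a NAS fall of at least 2 therefore satisfies 1A. The enumeration finds 0 transitions in 1B but not in 1A. It finds 281 in 1A without resolution, so the subset is strict.

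**4. Who fails both co-primaries.** For a resolver, NAS fall = B₀ + (I₀ − I₁) + (S₀ − S₁), where B₀ ≥ 1 and I₀ − I₁ ≥ 0. Any fall in steatosis grade gives a total of at least 2.

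| Steatosis grade in resolvers | Transitions | Fail both 1A and 1B |
|---|---|---|
| Falls | 70 | 0 |
| Unchanged | 34 | 2 |
| Rises | 32 | 12 |
| Total | 136 | 14 |

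The two failures with unchanged steatosis are S2/B1/I1 to S2/B0/I1 and S3/B1/I1 to S3/B0/I1. Of the 34 + 32 = 66 transitions without a steatosis fall, 66 − 14 = 52 still pass.

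**5. Recovering the composite.** Since 1B is the overlap of limbs A and B, responders to A or B = 1A + endpoint 10 − 1B. In patterns, 403 + 136 − 122 = 417, which is 14 more than 1A.

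**6. Direction.** The documents give no frequency for the lost class, so what follows is assumption only. Let it make up x_P of placebo and x_T of drug subjects, with composite rates of 20% and 40%. The 1A difference is then 20 points + x_P − x_T.

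| x_P | x_T | 1A difference | Power at 88/44 |
|---|---|---|---|
| 0 | 0 | 20 points | 80.6% |
| 4 points | 0 | 24 points | 93.5% |
| 4 points | 4 points | 20 points | 84.4% |
| 0 | 4 points | 16 points | 64.7% |

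The effect can go either way.

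**The case against.** The sponsor has a fair reply. Endpoint 1A is the Protocol's limb A unchanged, and 1B was already a Protocol secondary endpoint. Choosing stricter separate endpoints over a composite is partly a design decision. Section 11 does tell the reader that the primary endpoints changed, and the SAP must be final before unblinding. The subjects lost from the co-primaries still count in endpoints 10 and 15, and endpoint 10 is analysed by the primary method. The composite proportion in each arm follows from planned tables by step 5. The lost class may be very small.

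All of this stands, and it limits the size of the point. It does not supply the missing inference. A test of each limb separately is not a test of their union. The stratified CMH test needs counts by T2DM and fibrosis stage together, and SAP 7.2 breaks endpoint 10 down by fibrosis stage but not by T2DM. Nor does a note about an addition tell the reader that something was taken away.

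Three stronger readings are tempting, and the documents do not support them:

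- **The change favours the drug.** One might argue that a drug expected to lower liver fat leaves more resolvers with unchanged steatosis on placebo. But an effective drug also produces more resolvers overall, and no frequencies by arm are given.
- **The 2-point rule cancels the clause allowing any steatosis value.** It does so for 14 of 66 transitions, and 12 of those need steatosis to rise while ballooning clears.
- **The Protocol endpoint will have no result at all.** Its point estimate can be derived. Its test and interval are what is missing.

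**Conclusion.** The point holds as an omission and a disclosure fault. The Protocol's primary endpoint has no planned test or confidence interval, Section 11 does not state its replacement, and Section 4.3 leaves unclear which endpoint the 40% and 20% describe.

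The co-primary pair never credits resolution on its own. The Protocol responders who fail both are some, not all, of the resolvers without a fall in steatosis grade. Failing 1B alone is a different matter, since that also includes every NAS improver who does not resolve.

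The working rests on the entry rule that each component is at least 1 (a subject randomised in breach of it could be an exception), on steatosis grade rather than measured fat, and on no fibrosis worsening. Pattern counts are not patient frequencies. How many patients are affected, and which way the comparison would move, cannot be determined from the documents.

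**What to change.** - Add 1A OR endpoint 10 to SAP 5.1, 7.4 and 9.1.1, labelled as the Protocol-defined primary endpoint. Analyse it on ITT with the same stratified one-sided CMH test, confidence intervals and non-responder rule.
- State its role relative to 1A and 1B. SAP 7.3 tests both of those at 0.05 without adjustment, so the text must say which result decides success.
- Report by arm the number of resolvers without fibrosis worsening whose NAS fell by less than 2. This shows whether the change mattered.
- Correct Section 11 to say that the either/or primary was replaced.
- State in 4.3 which endpoint the 40% and 20% refer to.

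The cost is SAP wording and one table from data already collected. For the composite at these rates, the sample size of 162 stands. The downside is one more reported result, possibly less favourable than 1A or 1B.
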